9.6 Data management

The study database will be produced fully validated system which conforms to 21 Code of Federal Regulations Part 11 and includes a full electronic audit trail of the data and limits access to identified Data Management staff. Designated Investigator site staff will not be given access to the database until they have been trained. Data from the eCRFs will be entered into the study database by Investigator site staff using electronic verification. Automatic and manual validation programs will check for data discrepancies and, by generating appropriate error messages, allow the data to be confirmed or corrected before transfer of the data.

Subsequently, the entered data will be systematically checked by Data Management staff, using error messages printed from validation programs and database listings. Data errors or omissions will be entered on electronic Data Query Forms, which will be sent to investigational site staff who are required to respond to the query and confirm or correct the data. All relevant comments should be added to the eCRF using the Investigator Comment feature.

Data will be available to Novartis throughout the study for any recommendations regarding changes in conduct of the study. A Study Steering Committee may also be constituted for overseeing the conduct of the study and making any recommendations as needed.

Concomitant medications entered into the database will be coded using the WHO Drug Reference List, which employs the Anatomical Therapeutic Chemical classification system. Medical history/current medical conditions and AEs will be coded using MedDRA.

Data about the study drug dispensed to the patient will be tracked using the eCRF.

Over the course of the study, protocol deviations will be determined. The Investigator must certify that data entered into the eCRF system are complete and accurate. Quality control audits of all key safety and efficacy data in the database will be made prior to locking the database.

The QoL questionnaire (EQ-5D and SWB) can be recorded directly onto the eCRF.

After completing these actions and the database is complete and accurate, it will be locked and made available for data analysis. Any subsequent database changes require joint written agreement between the Clinical Trial Leader, the Trial Statistician, the Data Manager and the Quality Manager.

9.7 Data analysis

All analyses will be performed by Novartis or a contracted designee.

All the patients enrolled in the study will be analysed. The reference population for analysis will be patients who were enrolled and received follow-up, meeting eligibility criteria with at least one follow-up visit completed.

Each Investigator taking part in the study should enroll at least one patient and not more than 15 patients will be enrolled per centre. The enrolment period is one year, however this can be re-assessed depending on how recruitment is progressing. Data from all centres that participate in this protocol will be combined for analysis.

Descriptive statistics will be provided unless otherwise specified. These include n, mean, standard deviation, median and ranges for continuous, quantitative variables and frequencies and percentages for categorical, qualitative variables. For patients with screening assessments who do not enter the treatment period, data will only be listed. Further technical details and discussion of the following statistical considerations will appear in the statistical analysis plan, which will be finalised prior to database lock and the analysis.

For all analyses, baseline value will be defined as the latest assessment prior to first study drug administration.

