Data sources	Initiation of participating sites will be performed by Novartis or an appropriate third party. Before study initiation, a Novartis representative (or their designee) will review the protocol and electronic case report form (eCRF) with the physicians and their staff. Sites enrolling patients in this study will record data on the eCRFs which will capture, check, store and analyse the data. After the collection of informed consent and at enrolment into the study, patients will be assigned a unique subject number. All data collected will only be identified by the subject number and date of birth.
	Data will be collected from scans and laboratory reports captured within the medical notes of enrolled patients to determine baseline demographics and disease characteristics, exposure to study products and concomitant medication. Any history of stomatitis will also be captured along with potential predisposing factors.
	Changes in HRQoL will be assessed by the EQ-5D patient reported outcome questionnaire (Global Health Status QoL score). In addition, patients will be asked to complete four key subjective well-being questions taken from the Integrated Household Survey in England.
	Concomitant medications entered into the database will be coded using the World Health Organisation Drug Reference List, which employs the Anatomical Therapeutic Chemical classification system.
	Medical history/current medical conditions and AEs will be coded using the Medical dictionary for regulatory activities terminology.

Study size	Approximately two hundred patients will be studied across 25 centres, based on disease incidence, sample size in comparison with the overall population, and the expected recruitment within the enrolment period.
Data analysis	All analyses will be performed by Novartis or a contracted designee.
	population for analysis will be patients who were enrolled and received follow-up, meeting eligibility criteria with at least one follow-up visit completed.
	Data from all centres that participate in this protocol will be combined for analysis. All data will be analysed

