9.3.4.7 Study discontinuation

At a minimum, all patients who discontinue the study, whether withdrawn prematurely or otherwise and including those who refuse to return for a final visit, will be contacted for safety evaluations 30 days following end of treatment.

If a study withdrawal occurs, or if the patient fails to return for visits, the Investigator must determine the primary reason for a patient's premature withdrawal from the study and record this information on the End of Treatment eCRF page.

At this stage, the following information will be recorded:

- Date and reason for the end of the study (end of the study, treatment withdrawal, discontinuation of follow-up/lost to follow-up, or any other reason);
- Clinical details including best response during treatment;
- Safety data.

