9.5 Study size

The sample size calculation of 200 patients is based on disease incidence, sample size compared with the overall population, and the expected recruitment within the enrolment period.

The sample size is based on the precision of the estimate of the incidence of the two specific toxicities defined in the primary objective (stomatitis and NIP). Stomatitis is a common AE in patients treated with Afinitor with all grade incidences reported as 71% [Thanopoulou 2014], 59% [Yardley 2013] and 56% [Baselga 2012]. All grade incidences of NIP have been reported as 36% [Thanopoulou 2014], 16% [Yardley 2013], 12% [Baselga 2012] and 39% [Omarini et al 2014].

For a sample size of 200 completed patients, Table 9-4 shows the width of 95% CIs for a range of observed incidences in subjects treated with Afinitor in combination with exemestane for 12 months. For example, when the sample size is 200, an exact (Clopper Pearson) two-sided 95.0% CI for a single proportion will extend 6.8% below to 7.2% above the observed incidence for an expected incidence of 40%.

Table 9-4	Sample Size
N=200 Incidence N (%)	Exact (Clopper Pearson) 95% Cl
20 (10%)	6.2%, 15.0%.
40 (20%)	14.7%, 26.2%
60 (30%)	23.7%, 36.9%.
80 (40%)	33.2%, 47.2%
100 (50%)	42.9%, 57.1%
120 (60%)	52.9%, 66.9%
140 (70%)	63.1%, 76.3%
160 (80%)	73.8%, 85.3%

Sample size calculations were done using StatXact9[®].

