9.7.1 Analysis of the primary objective

The primary objective of this study is to evaluate (in patients commencing treatment with Afinitor in combination with exemestane for ABC after progression on a NSAI) two specific toxicities (stomatitis and NIP) in terms of: incidence, severity, length of time to onset, duration and clinical course, specific management (prophylaxis and intervention); and any preventive measures. Incidence, severity, length of time to onset, duration, and clinical course of any instances of stomatitis and/or NIP will be analysed. Specific management of these events, including variables for prophylaxis and interventions, and any preventive measures will also be investigated. Predisposing factors will also be investigated.

The analyses will be solely descriptive and comprise the description of the various items and the 95% CI.

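### Section 9.7 gives two incompatible analysis populations, and the restricted one makes the primary stomatitis and NIP denominator depend on completing a follow-up visit

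*Protocol*

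**What the plan says.** Section 9.7 of the protocol opens its account of who is analysed with "All the patients enrolled in the study will be analysed". The next sentence reads "The reference population for analysis will be patients who were enrolled and received follow-up, meeting eligibility criteria with at least one follow-up visit completed". The Data analysis entry of the abstract (Section 4) carries the same restriction. The only other group singled out is untreated: "For patients with screening assessments who do not enter the treatment period, data will only be listed".

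Sections 9.7.1 and 9.7.2 name no population of their own. Section 9.7.1 describes the target of the primary objective as two toxicities "in patients commencing treatment with Afinitor in combination with exemestane for ABC after progression on a NSAI", with no condition on returning to clinic.

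Sections 9.1 and 9.4 say that no visit schedule is imposed. Section 9.3.4 expects the first observation after about two weeks. Section 9.3.4.7 requires that all patients who discontinue the study, "including those who refuse to return for a final visit, will be contacted for safety evaluations 30 days following end of treatment". Section 11 accepts adverse events volunteered between visits and has them entered within 24 hours of the site learning of them.

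**The concern.** A safety incidence should be taken over everyone exposed. Completing a follow-up visit happens after exposure and can itself depend on toxicity, stopping treatment or death. A population defined by that visit is therefore no longer the population commencing treatment that the objective names.

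Two consecutive sentences also leave the analyst with two candidate denominators for the primary endpoint and no stated way to choose. If the restricted set is used, a treated patient whose event was reported by telephone, or found at the 30-day contact, leaves both numerator and denominator although the event is on record. Early deaths before any visit would leave the PFS analysis in the same way.

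**Working it through.** **1. The plan's own figure.** Section 9.5 states "For a sample size of 200 completed patients, Table 9-4 shows the width of 95% CIs for a range of observed incidences", and for 40% incidence "an exact (Clopper Pearson) two-sided 95.0% CI for a single proportion will extend 6.8% below to 7.2% above the observed incidence". Exact limits are lower = Beta(0.025; x, n-x+1) and upper = Beta(0.975; x+1, n-x). With x = 80 and n = 200 they are 33.15% and 47.15%, which agrees with the printed 33.2% and 47.2%. All eight rows of Table 9-4 reproduce to the printed decimal. No number in the table is disputed; the question is who is in the denominator.

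**2. Effect on precision.** At 40% incidence the exact interval is 33.0% to 47.3% with n = 190 and 32.8% to 47.6% with n = 180. The width barely changes, so the interval gives no warning that patients were dropped.

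**3. Effect on the estimate.** Let n = 200 treated patients with x events. Let k have no completed visit, e of whom had the event. Write p = x/n and q = e/k.

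- Restricted estimate = (x - e)/(n - k)
- Shift from the all-treated incidence = k(p - q)/(n - k)

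The estimate falls only if the excluded patients had events more often than all treated patients (q > p), and rises if less often.

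Inputs: p = 59% for stomatitis (x = 118) and p = 12% for NIP (x = 24), both among the reported incidences listed in Section 9.5. The protocol gives no value for k, so 4, 10 and 20 (2%, 5% and 10% of 200) are assumptions. The bounds set q to 100% and to 0%.

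| k | Stomatitis, all excluded had it | Stomatitis, none had it | NIP, all had it | NIP, none had it |
|---|---|---|---|---|
| 4 | 114/196 = 58.2% (-0.8) | 118/196 = 60.2% (+1.2) | 20/196 = 10.2% (-1.8) | 24/196 = 12.2% (+0.2) |
| 10 | 108/190 = 56.8% (-2.2) | 118/190 = 62.1% (+3.1) | 14/190 = 7.4% (-4.6) | 24/190 = 12.6% (+0.6) |
| 20 | 98/180 = 54.4% (-4.6) | 118/180 = 65.6% (+6.6) | 4/180 = 2.2% (-9.8) | 24/180 = 13.3% (+1.3) |

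**4. Which toxicity is more exposed.** Section 7.2.1 reports a 14% cumulative risk of grade 2 or higher stomatitis by two weeks in the earlier phase III trial, which is about when the first visit is expected. Section 7.2.2 reports few early NIP events and a 5% cumulative risk of grade 2 or higher at 12 weeks. Events before a first visit are thus realistic for stomatitis and much less so for NIP, and the large negative NIP bounds are unlikely in practice.

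**5. A check on the remedy.** Moving to all treated patients is not free of bias either. If 20 patients were never assessed after their first dose and are counted as event-free, 108/180 = 60% becomes 108/200 = 54%.

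**The case against.** A reader might infer that the rule discards the earliest toxicity cases and so biases incidence downward. The protocol does not support that in full.

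- **Who is lost.** Only patients with no completed visit at all are lost. Stomatitis in week 1 is kept if the patient attends at about two weeks. Stopping for toxicity will often produce a visit: Section 9.1 asks for an eCRF at extra visits, the Section 9.1 schedule records adverse events at end of treatment, and Section 9.3.4.8 asks discontinuing patients to return for an assessment. Whether that assessment or the 30-day contact counts as a follow-up visit is not defined.
- **Direction.** Patients without a visit also have little observed time and may have fewer recorded events, in which case the restriction raises the incidence.
- **What is known about them.** A reader might infer that all their events are on record. Section 9.3.4.8 says patients who withdraw consent are not contacted, and the 30-day contact cannot be relied on for deaths or losses to follow-up.
- **PFS.** The schedule collects PFS from month 3 and at end of treatment, so progression without any visit would rarely be recorded. Early deaths are the part that stands.
- **Milder reading.** The all-enrolled sentence could refer to patient accounting and the reference population to the main estimates. The text does not say so, and on that reading the primary safety analysis is still the restricted one.
- **Proportion.** The eligibility condition adds little, given the minimal criteria in Sections 9.2.1 and 9.2.2. With 10 excluded, the stomatitis shift is smaller than the roughly 7-point half-width in Table 9-4 at 60%. The analysis is descriptive.

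These points limit the scope, the certainty of direction and the size. They do not reconcile the two sentences or justify a visit-based denominator. Leaving technical detail to the SAP does not help either, because the protocol itself fixes the restricted set.

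A separate matter, not cured here: Section 11 counts adverse events from consent, which may come up to four weeks after treatment starts. That could affect more early events than the visit condition does.

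**Conclusion.** The point holds. The current text gives two incompatible populations, and the more specific one conditions the primary toxicity incidence on a post-exposure visit that the objective does not require.

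The size cannot be derived from the protocol. On the assumption that 10 of 200 treated patients have no completed visit, the extreme bounds are -2.2 to +3.1 points for stomatitis at 59% and -4.6 to +0.6 points for NIP at 12%. Understatement is plausible, chiefly for stomatitis, but is not established. What is certain is that the denominator is ambiguous and that the planned exact interval would not show the resulting shift.

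**What to change.** Change the wording in Section 9.7 and the abstract together:

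- Define the primary toxicity and PFS population as all enrolled patients who received at least one dose of Afinitor, regardless of visits completed. Count events from any source. List eligibility violators but keep them in.
- Report how many patients had no completed visit, with reasons, and how many had no post-dose safety information at all.
- Handle the latter group by censoring at last contact in a time-to-onset estimate, or by a sensitivity analysis, and do not silently count them as event-free.
- Keep the set with at least one completed visit for change from baseline in quality of life and as a sensitivity analysis. State whether the 30-day contact and the early discontinuation assessment count as a follow-up visit.

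No new data are needed. The cost is a little more analysis work and some patients with limited information in the denominator. It should be settled before database lock.

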9.7.1 Analysis of the primary objective

The primary objective of this study is to evaluate (in patients commencing treatment with Afinitor in combination with exemestane for ABC after progression on a NSAI) two specific toxicities (stomatitis and NIP) in terms of: incidence, severity, length of time to onset, duration and clinical course, specific management (prophylaxis and intervention); and any preventive measures. Incidence, severity, length of time to onset, duration, and clinical course of any instances of stomatitis and/or NIP will be analysed. Specific management of these events, including variables for prophylaxis and interventions, and any preventive measures will also be investigated. Predisposing factors will also be investigated.

The analyses will be solely descriptive and comprise the description of the various items and the 95% CI.

9.7.2 Analysis of secondary objectives

The key secondary objective of this study is to report the Afinitor and exemestane dosage/schedule in routine clinical practice, including the duration of exposure and the main reasons for any dose reduction or discontinuation of Afinitor.

- Duration of Afinitor and exemestane treatment: Number of treatment days will be calculated as the difference between the date of the first dose and one day after the date of the last dose of the study. The actual duration of treatment will be calculated as the difference between the exposure period minus the number of days on which treatment was temporarily withdrawn.
- Main causes of dose reduction, dose escalation or withdrawal of Afinitor and exemestane will be captured

The analyses will be solely descriptive and comprise the description of the various items and the 95% CI.

Further technical details and discussions including imputation and details regarding missing data will appear in the statistical analysis plan, which will be finalised prior to database lock and the analysis.

9.8 Quality control

Data entered into the 21 Code of Federal Regulations Part 11 compliant electronic database system will be validated against pre-defined criteria at the point of data entry and undergo source data verification procedures prior to further data review based on pre-defined validation rules established by Data Management. All data changes after initial data entry will be managed by data queries and have a full audit trail.

Further details regarding ensuring data quality and integrity will appear in the statistical analysis plan, which will be finalised prior to database lock and the analysis.

Data quality assurance

will assure database quality by reviewing the data entered into the eCRFs by investigational staff for completeness and accuracy, and in accordance with the data validation plan.

Data recording and document retention

In all scenarios, the physician must maintain source documents for each patient in the study, consisting of case and visit notes (hospital or clinic medical records) containing demographic and medical information, and the results of any other tests or assessments. All information entered in the eCRF must be traceable to these source documents in the patient's file. The physician must also keep the original informed consent form signed by the patient (a signed copy is given to the patient). The physician must give Novartis (or their designee) access to all relevant source documents to confirm their consistency with the eCRF entries. No information about the identity of the patients will be disclosed in source documents.

Site monitoring

Before study initiation or at a site initiation visit Novartis personnel will review the protocol and eCRFs with the Investigators and their staff. During the study, the field monitor will visit the site regularly to check the completeness of patient records, the accuracy of entries on the eCRFs, adherence to the protocol and Good Clinical Practice, progress of enrolment, and to ensure study treatment is being dispensed, and accounted for according to specifications. Key study personnel must be available to assist the field monitor during these visits. The Investigator must give the monitor access to all relevant source documents to confirm their consistency with the eCRF entries. Novartis monitoring standards require full verification for the presence of informed consent, adherence to the inclusion/exclusion criteria and documentation of SAEs. Formal site and compliance monitoring will be performed as described in the monitoring plan for this study which includes provisions for remote data monitoring, amendment of visit frequency due to common protocol deviations and anomalous data entries.

9.9 Limitations of the research methods

Being conducted solely in the UK means that the study results will only reflect the current status of clinical practice within the UK. Other countries will have different factors affecting their own clinical practice, such as re-imbursement issues and the availability of different competitor therapies.

10 **Protection of human subjects**

This clinical study was designed and will be implemented and reported in accordance with the International Conference on Harmonisation (ICH) Harmonised Tripartite Guidelines for Good Clinical Practice, with applicable local regulations, including the amended Medicines for Human Use (Clinical Trial) Regulations and the European Directive 2001/20/EC & 2005/28/EC, and with the ethical principles laid down in the Declaration of Helsinki.

It is unlikely that the study will place any study patients at risk as a result of their participation.

Compliance with Novartis and regulatory standards provides assurance that the rights, safety, and well-being of patients participating in NISs are protected (consistent with the principles that have their origin in the Declaration of Helsinki) and that the study data are credible and responsibly reported.

This study was designed and will be implemented and reported in accordance with the Guidelines for Good Pharmacoepidemiology Practices of the International Society for Pharmacoepidemiology [ISPE 2008] and the Strengthening the Reporting of Observational Studies in Epidemiology guidelines [VonElm 2008].

Regulatory and ethical compliance

The protocol and the proposed informed consent form must be reviewed and approved by a properly constituted Independent Ethics Committee (IEC) before study start. A signed and dated statement that the protocol and informed consent have been approved by the IEC must be given to Novartis before study initiation. Prior to study start, the Investigator is required to sign a protocol signature page confirming his or her agreement to conduct the study in accordance with these documents and all of the instructions and procedures found in this protocol. The Investigator is also required to give access to all relevant data and records to Novartis monitors, auditors, Novartis Clinical Quality Assurance representatives, designated agents of Novartis, IECs and regulatory authorities as necessary.

Informed consent procedures

Eligible patients may only be included in the study after providing written (witnessed, where required by law or regulation), IEC-approved informed consent, or, if incapable of doing so,

after such consent has been provided by a legally acceptable representative of the patient. If a patient's representative gives consent, the patient should be informed about the study to the extent possible given his or her understanding. If the patient is capable of doing so, he or she should indicate assent by personally signing and dating the written informed consent document or a separate assent form. Informed consent must be obtained before any data are collected. The process of obtaining informed consent should be documented in the patient source documents. Patients can be consented up to four weeks after the initiation of Afinitor plus exemestane.

Novartis will provide to treating physicians or other involved medical professionals in a separate document a proposed informed consent form that complies with the Declaration of Helsinki and the appropriate regulatory requirements.

Amendments to the protocol

Protocol changes or additions can only be made in a written protocol amendment approved by Novartis and, if appropriate, the IEC. Only amendments required for patient safety may be implemented prior to IEC approval. However, the Investigator is expected to take any immediate action required for the safety of any patient included in this study, even if this action represents a deviation from the protocol, in which case, Novartis should be notified of this action and the IEC at the study site should be informed within 10 working days.

Discontinuation of the study

Novartis reserves the right to discontinue this study under the conditions specified in the clinical study agreement.

Publication of study protocol and results

Novartis assures that the key design elements of this protocol will be posted in a publicly accessible database such as www.clinicaltrials.gov. At study completion and finalisation of the study report, the results of this study will also be submitted for publication and/or posted in a publicly accessible database of clinical study results.

The terms applying to the scientific publication of the results and the authors participating in these publications and presentations will be defined by Novartis Pharma, which retains the copyright on all important publications, including translations into other languages.

Study documentation

Each participating site will maintain appropriate medical and research records for this trial, in compliance with Section 4.9 of the ICH E6 Good Clinical Practice, and regulatory and institutional requirements for the protection of confidentiality of subjects. As part of participating in a Novartis-sponsored study, each site will permit authorised Novartis representatives, IEC and regulatory authority to examine (and, when required by applicable law, to copy) clinical records for the purposes of quality assurance reviews, audits and evaluation of the study safety and progress.

Source data are all information, original records of clinical findings, observations, or other activities in a clinical trial necessary for the reconstruction and evaluation of the trial. Examples of these original documents and data records include, but are not limited to, hospital records, clinical and office charts, laboratory notes, memoranda, pharmacy dispensing records, recorded data from automated instruments, copies or transcriptions certified after verification as being accurate and complete, microfiches, photographic

negatives, microfilm or magnetic media, X-rays, and patient files and records kept at the pharmacy, at the laboratories, and medico-technical departments involved in the clinical trial.

Data collection is the responsibility of the clinical trial staff at the site under the supervision of the site Principal Investigator. The eCRF is the primary data collection instrument for the study. The Investigator should ensure the accuracy, completeness, legibility, and timeliness of the data reported in the eCRFs and all other required reports. Data reported on the eCRF, that are derived from source documents, should be consistent with the source documents or the discrepancies should be explained. All data requested on the eCRF must be recorded.

The Investigator or site should maintain the trial documents as specified in Essential Documents for the Conduct of a Clinical Trial (ICH E6 Section 8) and as required by applicable regulations and/or guidelines. The Investigator or site should take measures to prevent accidental or premature destruction of these documents.

Essential written and electronic documents should be retained for at least15 years from the completion of the Clinical Trial unless Novartis provides written permission to dispose of them, or requires their retention for an additional period of time because of applicable laws, regulations and/or guidelines.

Confidentiality

The Investigator must ensure anonymity of the patients; patients must not be identified by names in any documents submitted to Novartis. Signed informed consent forms and patient enrolment log must be kept strictly confidential to enable patient identification at the site.

Audits and inspections

Source data/documents must be available for inspections by Novartis or their designee, IECs or Health Authorities.

11 Management and reporting of adverse events

All AEs including SAEs and safety endpoints, where relevant, must be collected and recorded in the study database, irrespective of causal association. Adverse Drug Reactions (ADRs) occurring in association with exposure to a Novartis drug other than the Novartis drug of interest, can be reported to the local Health Authority in accordance with national regulatory requirements for individual case safety reporting or to Novartis DS&E as a spontaneous report.

Adverse events identified for non-Novartis products should be reported to the local health authority in accordance with national regulatory requirements for individual case safety reporting or the Marketing Authorisation Holder; these will not be recorded in the Novartis safety database.

Adverse event reporting

An AE is defined as the appearance of (or worsening of any pre-existing) undesirable sign(s), symptom(s), or medical condition(s) that occur after patient's signed informed consent has been obtained. Abnormal laboratory values or test results occurring after informed consent constitute AEs only if they induce clinical signs or symptoms, are considered clinically significant, require therapy (e.g. haematologic abnormality that requires transfusion or haematological stem cell support), or require changes in study medication(s).

Confidential

Medical conditions or diseases present before starting the study are only considered AEs if they worsen after starting the drug of interest. Adverse events that begin or worsen after the start of this study should be recorded in the AE eCRF. Conditions that were already present at the time of informed consent should be recorded in the Medical History eCRF. Adverse Event monitoring should be continued for at least 30 days following the end of the study. Adverse Events (including laboratory abnormalities that constitute AEs) should be described using a diagnosis whenever possible, rather than individual underlying signs and symptoms. When a clear diagnosis cannot be identified, each sign or symptom should be reported as a separate AE.

Adverse events will be assessed according to the CTCAE version 4.0. If CTCAE grading does not exist for an AE, the severity of mild, moderate, severe, and life-threatening, corresponding to grades 1-4, will be used. CTCAE grade 5 (death) will not be used in this study; rather, information about deaths will be collected on a death form.

An AE can, therefore, be any unfavourable and unintended sign (including an abnormal laboratory finding), symptom, or disease temporally associated with the use of Afinitor, whether or not related to the medicinal product(s).

The occurrence of AEs should be sought by non-directive questioning of the patient at each visit during the study. Adverse Events also may be detected when they are volunteered by the patient during or between visits or through physical examination, laboratory test, or other assessments. All AEs must be recorded on the AE eCRF with the following information:

- the severity grade (1-4);
- its relationship to the drug(s) of interest (suspected or not suspected);
- its duration (start and end dates or if continuing at final examination);
- whether it constitutes a SAE.

In addition, all reports of the following special scenarios are considered an AE irrespective of whether a clinical event has occurred:

- Drug-drug or drug-food interaction;
- Drug exposure during pregnancy;
- Drug use during lactation or breast-feeding;
- Lack of effectiveness;
- Overdose;
- Drug abuse and misuse;
- Drug maladministration or accidental exposure;
- Dispensing errors or medication errors;
- Off-label use;
- Withdrawal or rebound symptoms.

Any treatment of any AE should be recorded on the AE eCRF. Some examples of treatment to be recorded are: no action taken (i.e., further observation only); drug of interest dosage adjusted or temporarily interrupted; drug of interest permanently discontinued due to this AE; treatment medication adjusted; non-drug therapy given; patient hospitalised or patient's hospitalisation prolonged.

Once an AE is detected, it should be followed until its resolution or until it is judged to be permanent. Assessment should be made at each visit, or more frequently if necessary, of

any changes in severity, the suspected relationship to the drug of interest, the interventions required to treat it, and the outcome.

Information about AEs already known about the medicinal product can be found in the SmPC. This information will be included in the patient informed consent and should be discussed with the patient during the study as needed.

Information on all AEs is included in the individual patient eCRF which must be updated and committed in the study database within 24 hours of the site becoming aware of it. Information on non-serious AEs is then transferred from the study database to Novartis DS&E **Communication** on a weekly basis.

Serious adverse event reporting

A SAE is defined as an event which:

- Is fatal or life-threatening;
- Results in persistent or significant disability/incapacity;
- Constitutes a congenital anomaly or birth defect;
- Requires inpatient hospitalisation or prolongation of existing hospitalisation, unless hospitalisation is for:
 - Routine treatment or monitoring of the studied indication, not associated with any deterioration in condition;
 - Elective or pre-planned treatment for a pre-existing condition that is unrelated to the indication under study and has not worsened since the start of the drug of interest;
 - Social reasons and respite care without any deterioration in the patient's general condition;
- Is medically significant. This is defined as an event that jeopardises the patient or may require medical or surgical intervention to prevent one of the outcomes listed above. It may require treatment on an emergency outpatient basis for an event not fulfilling any of the definitions of a SAE given above and not resulting in hospital admission;
- Transmission of infectious agent by medicinal product.

For Afinitor the following AEs are of special interest for targeted follow-up and should be notified to Novartis Drug Safety and Epidemiology (DS&E) in the same manner as a SAE:

- Acute and congestive heart failure
- Developmental toxicity
- Afinitor amenorrhoea
- Afinitor reactivation, aggravation, exacerbation of background disease
- Afinitor NIP
- Afinitor severe infections including hepatitis reactivation
- Pregnancy and breast-feeding women
- Hypersensitivity including anaphylaxis
- Malignancy and neoplasm
- Renal impairment or failure.

To ensure patient safety, every SAE, regardless of causality assessment, occurring after the patient has provided informed consent and until 30 days after the patient has stopped study participation must be reported to Novartis within 24 hours of learning of its occurrence.

Any SAEs occurring after this 28 day period should only be reported to Novartis if the treating physician or other involved health care professional suspects a causal relationship to the drug of interest.

Recurrent episodes, complications, or progression of the initial SAE must be reported as a follow-up to the original episode, regardless of when the event occurs. This report must be submitted within 24 hours of the treating physician or other involved health care professional receiving the follow-up information. An SAE considered completely unrelated to a previously reported one should be reported separately as a new event.

Information about all SAEs is collected and recorded on the SAE Report Form. The treating physician or other involved health care professional must assess the relationship to the drug of interest, complete the SAE report form and send the completed signed form within 24 h to the local Novartis Drug Safety & Epidemiology (DS&E) Department.. The telephone number of the contact persons in the local department of DS&E, specific to the site, are listed in the treating physician or other involved health care health care professional folder provided to each site.

Follow-up information is collected and sent in the same manner as for the original SAE Report, using a new SAE form, stating that this is a follow-up to the previously reported SAE and giving the date of the original report. The follow-up information should describe whether the event has resolved or continues, if and how it was treated, and whether the patient continued or withdrew from study participation.

